2. SYNOPSIS

Name of Sponsor/Company: Mezzion Pharma Co. Ltd in partnership with Pediatric Heart Network (PHN)	Individual Study Table Referring to Part of the Dossier Volume: Page:	(For National Authority Use Only)
Name of Finished Product: Udenafil tablet 87.5 mg		
Name of Active Ingredient: Udenafil		
Title of Study: A Phase III Safety Extension Study of Udenafil in Adolescents with Single Ventricle Physiology After Fontan Palliation (FUEL Extension)		
Principal Investigator: Multicenter		
Investigators: A list of investigators and their curricula vitae are provided in Appendix 16.1.4 .		
Study center(s): 27 sites (25 United States, 2 Canada)		
Publications (reference): None		
Studied period (years): Date of first informed consent: 06 February 2017 Date of data cutoff: 31 August 2020	Phase of development: 3	
Objectives: 
Determine the safety of udenafil (87.5 mg twice daily [BID]) in an adolescent population with single ventricle congenital heart disease palliated with the Fontan procedure.Evaluate the pharmacodynamic profile of udenafil.		

Methodology:

This was a Phase 3, open-label extension, 12-month, multicenter study, with an option for up to an additional 36 months, to supplement the Phase 3 **Fontan Udenafil Exercise Longitudinal Assessment Trial (FUEL study)** by providing a more robust safety and side-effect profile of the use of udenafil in adolescents with Fontan physiology. An attempt was made to recruit all participants who completed the FUEL study (approximately 400 adolescents). If recruitment from the FUEL study was less than 300 subjects, additional adolescents with Fontan physiology (De Novo subjects) were identified through the review of clinical data records at each participating site until the minimum of 300 total subjects were enrolled.

Those who were interested were enrolled and consented at the first study visit by the study coordinator from each participating site. Screening and identification of potential subjects continued until enrollment was complete.

Subjects who agreed to participate had baseline testing performed to determine eligibility with inclusion/exclusion criteria. For subjects who participated in the FUEL study and continued on to this extension study, safety laboratory results from FUEL were accepted as meeting the inclusion criteria for FUEL Extension. For De Novo subjects, the baseline visit consisted of 2 parts, baseline testing and study drug initiation. These parts may have been combined into a single day or split into 2 days so long as the duration between the visits was no more than 7 days. Safety laboratory testing and pregnancy testing for female participants were performed. After safety laboratory testing, subjects performed an exercise test to maximal effort to be eligible for study drug initiation.

All enrolled subjects were provided with udenafil, at a dose of 87.5 mg BID, for the duration of the study. The first dose of study drug was administered at the clinic (Visit 1). Approximately 2 hours (\pm 30 minutes) post dosing, resting heart rate and blood pressure were measured, and the subject performed a self-limited 6-minute walk. A repeat heart rate and blood pressure were measured immediately following and approximately 2 hours (\pm 30 minutes) following the 6-minute walk. Subjects who had a drop in systolic blood pressure >20 mmHg from the pre- to post-6-minute walk measurement, or had a drop in systolic blood pressure below the 5th percentile for age, were excluded from receiving any further study drug. Continuing subjects were dispensed their initial supply of study medication and instructed to take 1 tablet orally BID.

Methodology (continued):

All subjects returned to the clinic at Week 52. In addition to clinic visits, study coordinators contacted each subject by telephone the day after the baseline visit to discuss any adverse events (AEs). Subjects were also contacted by telephone at Weeks 1, 2, 3, 4, 8, 13, 17, 21, 30, 34, 39, 43, and 47 to ensure the study drug was well tolerated, to monitor study drug adherence, record AEs and concomitant medications, and offer pregnancy counseling, if needed. Subjects were encouraged to notify the study coordinator between scheduled contact dates with any new onset symptoms or complications.

For subjects continuing in FUEL Extension beyond Week 52, telephone contact occurred monthly and 30 and 90 days following study drug discontinuation to ensure the study drug was well tolerated and record AEs.

In-clinic study visits included assessments of safety (AEs, concomitant medication use, vital signs, and clinical safety laboratory evaluations), efficacy (exercise testing, echocardiogram, EndoPAT®, brain natriuretic peptide, and quality of life measurements), and pharmacokinetics.

The duration of study drug dosing was 12 months, with an option to extend for up to an additional 36 months. When an individual subject completed the study, the subject's primary cardiologist was notified, and the study drug was stopped.

De Novo subjects who were not participants in the FUEL trial were given the opportunity to participate in the heart rhythm-monitoring subset of FUEL Extension. Optional heart rhythm monitoring was to include a 3- to 7-day baseline monitor and a 3-day steady-state monitor.

Number of patients (planned and analyzed):

Planned: 300 to 400 adolescents.

Analyzed: 301 adolescents for safety (at interim analysis).

Diagnosis and main criteria for inclusion:

1. Males and females with Fontan physiology who participated in the FUEL trial or, if they did not participate in FUEL, were 12 to less than 19 years of age at enrollment.
2. Current anti-platelet or anticoagulant therapy.

Test product, dose and mode of administration, batch number: Udenafil tablets 87.5 mg orally BID [name] Ltd.: Batches UDBT15-11 and UDBT15-12 Halo Pharmaceutical Canada, Inc.: Batch MP0220

Duration of treatment: 52 weeks, with an option to extend for up to an additional 36 months

Reference therapy, dose and mode of administration, batch number: None

Criteria for evaluation at interim analysis: Efficacy endpoints:
 
• Change in maximal VO₂ from baseline to Week 52• Change in VO₂ at ventilatory anaerobic threshold (VAT) from baseline to Week 52• Change in ventilatory equivalents of carbon dioxide (VE/VCO₂) at peak exercise from baseline to Week 52• Change in VE/VCO₂ at VAT from baseline to Week 52• Change in minute ventilation at peak exercise• Change in work rate at peak exercise from baseline to Week 52• Change in work rate at VAT from baseline to Week 52• Change in myocardial performance index (MPI) from baseline to Week 52

Safety: Adverse events, vital signs (blood pressure and heart rate), and concomitant medication use.


Statistical methods at interim analysis: The Safety population included all subjects who took at least 1 dose of study drug. The Efficacy population included all enrolled subjects who had baseline and Week 52 exercise capacity data for which site-based data quality assurance process was complete at data cut-off.

Three treatment groups were defined:
 
• Udenafil-Udenafil, which included subjects who received udenafil in the FUEL and FUEL Extension studies• Placebo-Udenafil, which included subjects who received placebo in the FUEL study and udenafil in FUEL Extension• De Novo: Subjects who did not participate in the FUEL study and received udenafil in FUEL Extension

For efficacy and safety summaries, the Placebo-Udenafil and De Novo groups were combined (denoted as Placebo/De Novo-Udenafil).

All summaries were descriptive. Descriptive statistics for categorical endpoints included the number and percent of subjects in each treatment group and category. Quantitative endpoints were summarized for each treatment group with the mean, median, standard deviation, minimum value, and maximum value. Missing data were not imputed.

Baseline was defined as the last measurement before receipt of udenafil in FUEL Extension. For the Udenafil-Udenafil group, change to Week 52 of FUEL Extension measures change in exercise capacity between 26 weeks and 78 weeks of udenafil treatment. This change represents persistence of initial effectiveness beyond 26 weeks. For the Placebo-Udenafil and De Novo groups, change to Week 52 of FUEL Extension measures change in exercise capacity from pre-udenafil to following 52 weeks of udenafil treatment.

Statistical methods (continued):

For each efficacy endpoint, descriptive statistics were summarized for baseline, Week 52, and Week 52 change from baseline. A 2-sided, 95% confidence interval was calculated for change from baseline for each group.

Safety analyses were descriptive with no formal hypothesis testing. All AEs were classified by the Medical Dictionary for Regulatory Activities with respect to system organ class and preferred term. Subject incidence of all treatment-emergent adverse events (TEAEs), and TEAEs that are treatment-related, serious, serious treatment-related, and any TEAE leading to study discontinuation were tabulated. Number (%) of subjects who were hospitalized, had a cardiac transplant, or died were tabulated.

Incidence of potentially clinically significant changes from pre dose values in blood pressure and heart rate were tabulated at i) post first study dose but before the self-limited 6-minute walk, ii) after the 6-minute walk, and iii) at any time after dosing.

SUMMARY – CONCLUSIONS

EFFICACY RESULTS:

For the Udenafil-Udenafil group, change to Week 52 of FUEL Extension measures change in exercise capacity between 26 weeks and 78 weeks of udenafil treatment. This change represents persistence of initial effectiveness beyond 26 weeks. For the Placebo/De Novo-Udenafil group, change to Week 52 of FUEL Extension measures change in exercise capacity from pre-udenafil to after 52 weeks of udenafil treatment.

In the Placebo/De Novo-Udenafil group, mean exercise capacity and myocardial performance improved between pre-udenafil and after 52 weeks of udenafil treatment:

- Mean increase at peak exercise effort in VO₂ (58.00 mL/min), work rate (5.78 watts), and minute ventilation (2.41 L/min). When VO₂ was standardized by each subject's body weight, a mean decrease was observed (-0.93 mL/kg/min; 95% CI: -1.7 to -0.2 mL/kg/min).
- Mean increase in VO₂ at VAT of 12.90 mL/min (95% confidence interval [CI]: -23.1 to 48.9 mL/min). When standardized by each subject's body weight, a mean decrease was observed (-0.93 mL/kg/min; 95% CI: -1.5 to -0.4 mL/kg/min).
- Mean decrease in VE/VCO₂ at VAT of -0.77 (95% CI: -1.4 to -0.2).
- Mean increase in work rate at VAT of 0.58 watts (95% CI: -2.6 to 3.7 watts).
- Mean decrease in MPI of -0.04 (95% CI: -0.1 to 0.0).

In the Udenafil-Udenafil group, mean exercise capacity was improved while myocardial performance did not deteriorate between 26 weeks and 78 weeks of udenafil treatment:

- Mean increase at peak exercise effort in VO₂ (38.00 mL/min), work rate (2.99 watts), and minute ventilation (2.56 L/min). When VO₂ was standardized by each subject's body weight, a mean decrease was observed (-1.45 mL/kg/min; 95% CI: -2.3 to -0.6 mL/kg/min).
- Mean increase in VO₂ at VAT of 6.57 mL/min (95% CI: -47.9 to 61.0 mL/min). When standardized by each subject's body weight, a mean decrease was observed (-1.25 mL/kg/min; 95% CI: -2.1 to -0.4 mL/kg/min).
- Mean decrease in VE/VCO₂ at VAT of -0.66 (95% CI: -1.6 to 0.3).
- Mean increase in work rate at VAT of 0.26 watts (95% CI: -5.1 to 5.6 watts).
- Negligible mean decrease in MPI of -0.0 (95% CI: 0.0 to 0.0).

SAFETY RESULTS:

No clinically important differences were observed in the safety profile between subjects who had previously received treatment with udenafil and those who were naïve to udenafil treatment prior to participating in this study.

Similar percentages of subjects in the Udenafil-Udenafil and Placebo/De Novo-Udenafil groups reported TEAEs (77.3% and 80.3%, respectively), drug-related TEAEs (64.1% and 67.6%, respectively), TEAEs of Grade ≥ 3 (3.9% and 7.5%, respectively), serious TEAEs (10.9% and 13.9%, respectively), drug-related serious TEAEs (3.9% and 5.8%, respectively), and TEAEs resulting in temporary or permanent discontinuation of study drug (15.6% and 12.7%, respectively).

The most common TEAEs reported included headache (35.2%), flushing (17.2%), dizziness (11.7%), upper respiratory tract infection (10.2%), and nausea (10.2%) in the Udenafil-Udenafil group and headache (40.5%), flushing (15.6%), nasopharyngitis (12.7%), and dizziness (12.7%) in the Placebo/De Novo-Udenafil group. Most TEAEs were mild or moderate in intensity; similar percentages of subjects in the Udenafil-Udenafil (5 subjects; 3.9%) and Placebo/De Novo-Udenafil (13 subjects; 7.5%) groups experienced a severe TEAE.

There was no clinically important difference in the TEAE profile among males and females; the limited number of non-Caucasian subjects and Hispanic or Latino/Latina subjects precluded meaningful comparisons between race and ethnicities within treatment groups.

No subject died during the study. At least 1 serious TEAE was reported by 14 (10.9%) subjects in the Udenafil-Udenafil group and 24 (13.9%) subjects in the Placebo/De Novo-Udenafil group. Among the serious TEAEs reported, cardiac failure was reported by 4 subjects in the Placebo/De Novo Udenafil group, transient ischaemic attack was reported by 2 subjects in the Placebo/De Novo Udenafil group and 1 subject in the Udenafil-Udenafil group, abdominal pain and appendicitis were reported by 2 subjects each in the Udenafil-Udenafil group, protein-losing gastroenteropathy, gastroenteritis, and syncope were reported by 2 subjects each in the Placebo/De Novo Udenafil group, and anaemia, supraventricular tachycardia, ventricular tachycardia, and vomiting were reported by 1 subject each in the Udenafil-Udenafil and Placebo/De Novo Udenafil groups. All other serious TEAEs were reported by no more than a single subject in either treatment group. Hospitalization was reported for 14 (10.9%) subjects in the Udenafil-Udenafil group and for 24 (13.9%) subjects in the Placebo/De Novo Udenafil group. No transplants were reported.

At least 1 TEAE leading to temporary or permanent discontinuation of study drug was reported by 20 (15.6%) subjects in the Udenafil-Udenafil group and 22 (12.7%) subjects in the Placebo/De Novo-Udenafil group. The most common types of TEAEs that led to temporary or permanent discontinuation of study drug were associated with nervous system disorders including headache (2 Udenafil-Udenafil, 4 Placebo/De Novo-Udenafil), migraine (2 Udenafil-Udenafil, 2 Placebo/De Novo-Udenafil), and dizziness (1 Udenafil-Udenafil, 2 Placebo/De Novo-Udenafil). Dizziness was the most commonly reported TEAE of special interest (11.7% Udenafil-Udenafil and 12.7% Placebo/De Novo-Udenafil). None of the events of dizziness was serious, all were considered mild or moderate in intensity and most required no change in study drug. The other TEAEs of interest including syncope, presyncope, and hypotension occurred in <4% of subjects in either treatment group.

No clinically important findings were observed in the evaluations of vital signs.

CONCLUSION:

Improvement in exercise capacity was observed in those who were previously naïve to udenafil therapy, and there was persistence of effect on exercise capacity for those who were previously treated with udenafil. Udenafil administered orally at 87.5 mg BID for 52 weeks was safe and well tolerated in this study.

Date of the report: 25 February 2021

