9.3.2 Exclusion Criteria

Subjects were excluded if they met any of the following criteria:

1. Weight <40 kg.
2. Height <132 cm.
3. Hospitalization for acute decompensated heart failure within the last 12 months.
4. Current intravenous inotropic drugs.
5. Undergoing evaluation for heart transplantation or listed for transplantation.
6. Diagnosis of active protein-losing enteropathy or plastic bronchitis within the last 3 years or a history of liver cirrhosis.
7. Known Fontan baffle obstruction, branch pulmonary artery stenosis, or pulmonary vein stenosis resulting in a mean gradient of >4 mmHg between the regions proximal and distal to the obstruction as measured by either catheterization or echocardiography, obtained prior to screening for the study.
8. Single lung physiology with greater than 80% flow to one lung.
9. Maximal VO₂ less than 50% of predicted for age and gender at enrollment.
10. Severe ventricular dysfunction assessed qualitatively by clinical echocardiography within 6 months prior to enrollment.
11. Severe valvar regurgitation, ventricular outflow obstruction, or aortic arch obstruction assessed by clinical echocardiography within 6 months prior to enrollment.
12. Significant renal (serum creatinine >2.0 mg/dL), hepatic (serum aspartate aminotransferase and/or alanine aminotransferase >3 times upper limit of normal), gastrointestinal or biliary disorders that could impair absorption, metabolism or excretion of orally administered medications, based on laboratory assessment 6 weeks prior to screening for the study.
13. Inability to complete exercise testing at baseline screening.
14. History of PDE-5 inhibitor use within 3 months before study onset.

15. History of any other medication for treatment of pulmonary hypertension within 3 months before study onset.
16. Known intolerance to oral udenafil.
17. Frequent use of medications or other substances that inhibit or induce cytochrome P450 (CYP)3A4.
18. Current use of alpha-blockers or nitrates.
19. Ongoing or planned participation in another research protocol that would either prevent successful completion of planned study testing or invalidate its results.
20. Noncardiac medical, psychiatric, and/or social disorder that would prevent successful completion of planned study testing or would invalidate its results.
21. Cardiac care, ongoing or planned, at a non-study center that would impede study completion.

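### The FUEL Extension synopsis lists safety laboratories among its clinic assessments but leaves them out of the interim safety criteria, methods and results, and still draws an unqualified 52-week safety conclusion.

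*Protocol*

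**What the plan says.** The Protocol document opens with the synopsis of an interim report on FUEL Extension. The sections that follow report the 26-week parent trial, FUEL, and the SAP is also FUEL's. For the extension, only the synopsis is available.

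- **Collection.** Under Methodology: "In-clinic study visits included assessments of safety (AEs, concomitant medication use, vital signs, and clinical safety laboratory evaluations". On timing: "All subjects returned to the clinic at Week 52". For subjects rolling over from FUEL, "safety laboratory results from FUEL were accepted as meeting the inclusion criteria for FUEL Extension"; De Novo subjects had their own baseline testing.
- **Interim safety criteria.** The whole entry is "Adverse events, vital signs (blood pressure and heart rate), and concomitant medication use".
- **Methods.** "Safety analyses were descriptive with no formal hypothesis testing". The planned displays cover treatment-emergent adverse events (TEAEs), hospitalization, transplant, death, and blood pressure and heart rate changes.
- **Population.** "Analyzed: 301 adolescents for safety (at interim analysis".
- **Conclusion.** "Udenafil administered orally at 87.5 mg BID for 52 weeks was safe and well tolerated in this study".

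**The concern.** Safety is the extension's first stated objective, and the study was set up to enlarge the safety profile beyond 26 weeks. A general safety conclusion should rest on all the safety data the study says it collected, or say which part it leaves out. Here one of the four listed components drops out between the description of the visits and the analysis, without comment.

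Laboratories are also the component least replaceable by the others. Week 52 is the only post-baseline clinic visit the synopsis describes; the scheduled contacts in between, and those after Week 52, are by telephone. A chemistry change without symptoms would not be expected to enter the adverse event tables through a telephone call. Someone relying on the conclusion would not learn from the synopsis that laboratory results form no part of its stated basis.

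**Working it through.** **1. The plan's own figure.** The safety N can be recovered from the counts and percentages in the synopsis.

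- Udenafil-Udenafil: 5/128 = 3.9%, 14/128 = 10.9%, 20/128 = 15.6%.
- Placebo/De Novo-Udenafil: 13/173 = 7.5%, 24/173 = 13.9%, 22/173 = 12.7%.

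In a search from 50 to 300, 128 and 173 are the only denominators that fit all three percentages in their group, and 128 + 173 = 301, as stated. The adverse event summaries therefore cover the full safety population. The gap lies in the type of data reported, not in the count of subjects.

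**2. The four listed assessments traced through the synopsis.**

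| Safety assessment at clinic visits | Interim criteria | Methods | Results |
|---|---|---|---|
| Adverse events | yes | yes | yes |
| Vital signs | yes | yes | yes |
| Concomitant medication | yes | none described | none described |
| Safety laboratories | **no** | **no** | **no** |

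Laboratories are the only listed assessment missing from the criteria. Concomitant medication is in the criteria but has no display in the synopsis; that is a lesser matter, since it is not itself a measure of harm.

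**3. The standard set in the parent trial.**

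- FUEL SAP section 2.0 names clinical laboratory tests as one of three safety monitoring sources.
- SAP section 6.5.3 requires change from baseline and treatment-emergent abnormalities.
- Report sections 12.4.2.1 and 12.4.2.2 (Tables 39 and 40) give ALT, AST and creatinine.
- The FUEL conclusions (sections 12.6 and 13) mention laboratory findings explicitly. The extension conclusion does not.

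**4. The laboratory evidence that exists.** In FUEL, 189 of 200 udenafil subjects (94.5%) had Week 26 values. No subject reached Grade 3 ALT or AST. Shifts from normal to above the upper limit on udenafil, with exact (Clopper-Pearson) two-sided 95% limits:

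- ALT 2/189 = 1.1% (0.1% to 3.8%)
- AST 5/189 = 2.6% (0.9% to 6.1%)
- Creatinine 0/189 (upper limit 1 − 0.025^(1/189) = 1.9%)

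These describe 26 weeks of exposure. Extension Week 52 is 52 weeks on udenafil for the Placebo/De Novo group and 26 + 52 = 78 weeks for Udenafil-Udenafil. For that period the documents give neither a laboratory numerator nor a denominator, so no rate or confidence limit can be calculated.

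**The case against.** The strongest reply is that an interim synopsis is a selective summary. It also leaves EndoPAT, BNP, quality of life and pharmacokinetics out of the interim criteria, so laboratories were not singled out. The extension's own protocol, SAP and tables are not available, and laboratories may have been tabulated there or held for the final report.

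Much of this stands, and it rules out several stronger readings.

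- **Hepatic and renal safety is claimed without data.** A reader might infer this, but the conclusion is general and names no organ or laboratory value. Adverse event reporting in 301 subjects could pick up clinical hepatic or renal events, and 26-week chemistry exists from FUEL.
- **The laboratories were never examined.** A synopsis can show only that they are not reported in it.
- **The exclusion criteria show that organ toxicity was feared.** Criterion 12 in section 9.3.2 covers renal and hepatic disorders along with "gastrointestinal or biliary disorders that could impair absorption, metabolism or excretion of orally administered medications". Its stated rationale is drug handling. It is also a FUEL criterion; the extension's full exclusion list is not in the documents.
- **Zero events at Week 52 would give a particular bound.** The number of Week 52 samples is not stated, so any such bound would be conjecture.

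What the reply does not answer is the mismatch inside the synopsis. The other omitted assessments do not bear on a safety conclusion; laboratories do. If they were deferred, the synopsis should say so, and the conclusion should be worded to match.

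**Conclusion.** The point holds as a reporting and scope gap. The synopsis describes four safety assessments, carries three into its interim criteria, gives no reason or deferral for the fourth, and concludes on safety without qualification. No laboratory result is reported for any of the 301 subjects, and the documents contain no udenafil chemistry beyond Week 26.

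Two assumptions sit underneath. The extension synopsis does not name its analytes; ALT, AST and creatinine are presumed from the FUEL panel. Laboratory sampling at Week 52 is inferred from the general statement about clinic visits together with the Week 52 return visit. If either is wrong, the tables proposed below would change, but the need to qualify the conclusion would remain. Nothing here suggests that udenafil caused a laboratory abnormality; the documents do not allow that to be judged either way after Week 26.

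**What to change.** Preferred: add the collected safety laboratories to the interim safety criteria. Report by group the number with data, baseline, Week 52, change, and shifts from normal to above the upper limit of normal. For Udenafil-Udenafil, optionally also show change from the FUEL pre-treatment value, because the extension baseline in that group already follows 26 weeks of drug and change from it would miss any earlier shift.

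Alternative: limit the conclusion to adverse events and vital signs over 52 weeks, state that laboratory results are not reported in this interim synopsis, and say where or when they will be.

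The cost is one or two descriptive tables, for which FUEL Tables 14.3.21 and 14.3.22 offer a ready layout if the panel is the same, or a somewhat narrower safety statement. No new data collection is needed if the Week 52 samples were taken as the synopsis implies.

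### The extension's interim efficacy results rest on Week 52 completers with site-verified tests, but the conclusions are not limited to them and the synopsis gives no efficacy n

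*Protocol*

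**What the plan says.** All the extension text is in the Protocol document, Section 2 (Synopsis). The report body and the SAP describe the 26-week FUEL trial.

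- **Population** (Statistical methods at interim analysis): the Efficacy population is enrolled subjects who "had baseline and Week 52 exercise capacity data for which site-based data quality assurance process was complete at data cut-off".
- **Missing data** (same place): "Missing data were not imputed".
- **Estimation** (same place): "A 2-sided, 95% confidence interval was calculated for change from baseline for each group".
- **Numbers** (Number of patients): "Analyzed: 301 adolescents for safety (at interim analysis"). No corresponding figure is given for efficacy, and the Efficacy Results list means and intervals without n or SD.
- **Conclusion**: exercise capacity is said to have improved in subjects new to udenafil, and "there was persistence of effect on exercise capacity for those who were previously treated with udenafil". Neither statement mentions the Efficacy population.

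**The concern.** Membership of this population depends on what happened after baseline. A subject drops out of every efficacy row by stopping before Week 52, missing the test, not having reached Week 52 by the cut-off of 31 August 2020, or attending a site whose checks were unfinished. The first two reasons can be related to how the subject was doing. The last two are largely administrative.

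The synopsis reports adverse events leading to temporary or permanent discontinuation of study drug in "20 (15.6%) subjects in the Udenafil-Udenafil group and 22 (12.7%) subjects in the Placebo/De Novo-Udenafil group", and serious cardiac failure in 4 Placebo/De Novo subjects. It does not say how many of them had a verified Week 52 test. FUEL handled the same problem differently: it analysed all randomised subjects and carried values forward for maximal VO2 (Sections 9.7.1.1 and 9.7.1.4.4).

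The persistence claim is the one most exposed. If those whose exercise capacity fell were less likely to be tested at Week 52, stability among the tested would overstate stability in the group. This is separate from the absence of a control arm.

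**Working it through.** **Step 1. Group sizes.** Serious adverse events are reported for "14 (10.9%) subjects in the Udenafil-Udenafil group and 24 (13.9%) subjects in the Placebo/De Novo-Udenafil group", and the discontinuation counts quoted above give a second pair of percentages.

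- 14/128 = 10.9% and 20/128 = 15.6%
- 24/173 = 13.9% and 22/173 = 12.7%

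Searching 100 to 200, these are the only denominators that fit. Their sum, 128 + 173 = 301, reproduces the stated safety number. (FUEL Table 5 shows 126 udenafil subjects continuing into the extension; the two counts should be reconciled.)

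**Step 2. What the interval widths imply.** Assuming t intervals for a mean change, half-width = t(0.975, n−1) × SD / √n. Neither n nor SD is printed, so SD must be assumed. I borrow the FUEL 26-week SDs of change and pool the two arms as √[(a² + b²)/2].

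- VO2 at VAT, mL/min: 185.191 and 193.508 (Table 12, observed cases), pooled 189.4
- VO2 at VAT, mL/kg/min: 2.998 and 3.216 (Table 15), pooled 3.11
- VE/VCO2 at VAT: 3.564 and 2.967 (Table 17), pooled 3.28
- Work rate at VAT, W: 15.076 and 13.246 (Table 17), pooled 14.2
- Peak VO2, mL/kg/min: 4.056 and 3.672 (Table 13), pooled 3.87

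Example of a half-width, from the Udenafil-Udenafil results: "Mean increase in work rate at VAT of 0.26 watts (95% CI: -5.1 to 5.6 watts") gives (5.6 + 5.1)/2 = 5.35.

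Example of a solution, VO2 at VAT in mL/min: with n = 49, 2.011 × 189.4 / 7 = 54.4, against a printed half-width of (61.0 + 47.9)/2 = 54.45.

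| Udenafil-Udenafil endpoint | Half-width | Implied n of 128 | n if SD × 1.25 | SD needed for n = 65 | Ratio to FUEL SD |
|---|---|---|---|---|---|
| VO2 at VAT, mL/min | 54.45 | 49 | 75 | 219.7 | 1.16 |
| VO2 at VAT, mL/kg/min | 0.85 | 54 (48–60 with rounding) | 83 | 3.43 | 1.10 |
| VE/VCO2 at VAT | 0.95 | 48 (44–53) | 74 | 3.83 | 1.17 |
| Work rate at VAT, W | 5.35 | about 30 | 45 | 21.6 | 1.52 |
| Peak VO2, mL/kg/min | 0.85 | 82 (73–92) | 127 | 3.43 | 0.89 |

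**Step 3. How stable is this?** The VAT rows should have nearly equal n; FUEL's udenafil arm had 170 for VO2 and VE/VCO2 and 167 for work rate. Here they give 30 to 54, so the FUEL SDs cannot all carry over. A modest increase moves three of the four rows past half of 128.

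**Step 4. A check without FUEL SDs.** Suppose both extension groups share one SD and all 173 Placebo/De Novo subjects were included. The Placebo/De Novo half-widths (36.0 mL/min; 3.15 W) then fix that SD at 239.9 mL/min and 21.0 W, and cap Udenafil-Udenafil at about 77 (VO2 at VAT) and 62 (work rate) of 128. The cap scales with the square of the SD ratio. FUEL's own arms differed for work rate by 15.076/13.246 = 1.138. Squared, that is 1.295, and 62 × 1.295 = 80. This check does not settle the matter either.

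**The case against.** The synopsis openly states the population rule and the lack of imputation, and calls the analysis interim. Only a synopsis of the extension is available, so the full extension report may well hold n, SD and disposition. Finishing site checks is an administrative condition with no shown link to a subject's response. Dropout may be small: 4.5% discontinued FUEL (Table 5). Limiting efficacy to verified tests is also in keeping with FUEL's own practice of blinded review and consensus (Section 9.5.1.1.1). All of this is fair. It means the direction and size of any bias are unknown.

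A reader might infer three stronger things that the documents do not support.

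- **That the results come from a minority of the Udenafil-Udenafil group.** This depends on 26-week SDs applied to a 52-week change. It also mixes observed-case SDs for one row with carried-forward SDs for the others, although the extension imputed nothing. In FUEL the observed-case SDs for VO2 at VAT were about 5 to 6% larger (185.2 against 177.0; 193.5 against 183.0).
- **That the site-checking rule caused the low VAT numbers.** The same rule leaves about 82 of 128 for peak VO2 per kg. FUEL lacked paired VO2 at VAT in 21% of participants against 5% for maximal VO2 (Section 11.4.7), so undeterminable VAT is an obvious contributor.
- **That the conclusions claim to cover all treated subjects.** They do not say so; they are simply unqualified.

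What remains standing is the mismatch between a selected population and an unrestricted conclusion.

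**Conclusion.** The point holds without any assumption in its core: efficacy is summarised only for subjects with paired, site-verified tests, nothing is imputed, the synopsis gives no efficacy n, and the conclusions on improvement and persistence carry no such limit.

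The share included is unknown. Conditional on FUEL SDs it would be about 30 to 54 of 128 (23 to 42%) for the VAT endpoints and about 82 of 128 (64%) for peak VO2 per kg. SDs larger by 10 to 17%, or 52% for work rate, would put the VAT rows above half. These figures show why n must be reported; they do not show that most subjects were left out. Nor is it shown that the selection favoured udenafil, only that the synopsis gives no means of ruling this out.

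**What to change.** 1. Limit the efficacy conclusions to Week 52 completers with verified tests.
2. Report n and SD for each endpoint and group. Give the reasons for exclusion, separating early stopping, Week 52 missed or not yet reached, VAT not determinable, and site checks unfinished. Tabulate baseline values of included against excluded subjects.
3. Add an analysis that uses every subject with a baseline value, for example a likelihood-based model of baseline and Week 52, with a carried-forward sensitivity analysis in the manner of FUEL.
4. Repeat it when site checks are complete. Until then, use tests not yet cleared only in a sensitivity analysis, since including them trades data quality for completeness.

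The cost is a few tables and some re-analysis of existing data, with possibly less favourable results. There is a limit to what step 3 can do: with a single follow-up test, the model corrects only for selection related to baseline, not for dropout that depends on the unseen Week 52 value.
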